5.4.1 Primary Efficacy Assessment

The primary endpoints are OS in participants with PD-L1 CPS ≥ 20 and all randomized participants. See [Section 8.3.1](#) for the definitions of OS. Every effort will be made to collect survival data on all participants including participants withdrawn from treatment for any reason, who are eligible to participate in the study and who have not withdrawn consent for survival data collection. If the death of a participant is not reported, all dates in this study representing a date of participant contact will be used in determination of the participant's last known date alive.

5.4.2 Secondary Efficacy Assessment

Secondary efficacy endpoints include OS in selected subgroups and ORR in participants with PD-L1 CPS ≥ 20 and in all randomized participants. See [Section 8.3.2](#) for the definition of ORR. All randomized participants will be monitored by radiographic assessment every 6 weeks (± 1 week) for the first 12 months (until Week 48) and every 12 weeks (± 1 week) until progression or treatment is discontinued, whichever occurs later, [beginning from the first on-study assessment on Week 6 (± 1 week)], to determine changes in tumor size. RECIST 1.1 criteria will be used for the assessment.

The assessments of progression from the blinded independent central review (BICR) will be used for the principal analyses of PFS.

The assessments of best overall response from the blinded independent central review (BICR) will be used for the principal analyses of ORR. For details regarding response criteria using RECIST 1.1 refer to [Appendix 3](#).

5.5 Pharmacokinetic Assessments

Samples for PK and immunogenicity assessments will be collected for all participants receiving nivolumab and ipilimumab as described in [Table 5.5-1](#). All time points are relative to the start of study drug administration. All on-treatment time points are intended to align with days on which study drug is administered, if dosing occurs on a different day, the PK and immunogenicity sampling should be adjusted accordingly. Further details of sample collection, processing, and shipment will be provided in the laboratory procedures manual.

Pharmacokinetic and Immunogenicity Collection and Processing

A detailed schedule of PK and immunogenicity evaluations is provided in [Table 5.5-1](#). PK samples will be analyzed for nivolumab/ipilimumab by a validated ligand binding assay. Immunogenicity samples will be analyzed for anti-nivolumab antibodies / anti-ipilimumab antibodies by a validated immunogenicity assay; samples may also be analyzed for neutralizing antibodies by a validated method. Serum samples may be analyzed by an exploratory method that measures anti-drug antibodies for technology exploration purposes; exploratory results will not be reported. Serum samples designated for PK or biomarker assessments may also be used for immunogenicity analysis if required (eg, insufficient volume for complete immunogenicity assessment or to follow up on suspected immunogenicity related AE).

Table 5.5-1: Pharmacokinetic (PK) and Immunogenicity Sample Collections for Nivolumab and Ipilimumab (Arm A)

Study Day ^a (1 Cycle = 6 weeks)	Event (Relative To Dosing) Hour	Time (Relative To Dosing) Hour: Min	Pharmacokinetic Blood Sample for Nivolumab	Immunogenicity Blood Sample for Nivolumab	Pharmacokinetic Blood Sample for Ipilimumab	Immunogenicity Blood Sample for Ipilimumab
C1D1 (Nivolumab dose 1 & Ipilimumab dose 1)	Predose ^b	00:00	X	X	X	X
C1D1	0.5 (EOI) ^c	See footnote c	X		X	
C1D15 (Nivolumab dose 2)	Predose ^b	00:00	X	X	X	X
C2D15 (Nivolumab dose 5)	Predose ^b	00:00	X	X	X	X
C4D15 (Nivolumab dose 11)	Predose ^b	00:00	X	X	X	X
D15 of every 4th cycle after C4D15 until end of study treatment or maximum up to two years of treatment	Predose ^b	00:00	X	X	X	X

^a If ipilimumab is discontinued and nivolumab continues, ipilimumab PK and ADA should be collected only for the next 2 time points (corresponding to nivolumab sample collection) according to the PK table.

^b Predose samples should be taken prior to the start of the first drug (preferably within 30 minutes). If it is known that a dose is going to be delayed, then the predose sample should be collected just prior to the delayed dose. However, if a predose sample is collected but the dose is subsequently delayed, an additional predose sample should not be collected.

^c EOI: End of Infusion. This sample should be collected at the end of infusion of the second drug administered. If the end of infusion is delayed to beyond the nominal infusion duration, the collection of this sample should also be delayed accordingly. EOI samples may not be collected from the same IV access as drug was administered.

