4.5 Selection and Timing of Dose for Each Participant

The dosing schedule is detailed below in [Table 4.5-1](#).

All participants will be monitored continuously for AEs while on study treatment. Treatment modifications (eg, dose delay, reduction, retreatment, or discontinuation) will be based on specific laboratory and adverse event criteria, as described in [Sections 4.5.2, 4.5.3, 4.5.4, and 4.5.5](#).

Table 4.5-1: Dosing Schedule (Arm A 1 Cycle = 6 weeks, Arm B 1 Cycle = 3 weeks)

	Week 1 ± 3 Days ^d	Week 2 ± 3 Days ^d	Week 3 ± 3 Days ^d	Week 4 ± 3 Days ^d	Week 5 ± 3 Days ^d	Week 6 ± 3 Days ^d
Arm A: ^a Nivolumab 3 mg/kg Q2W + Ipilimumab 1 mg/kg Q6W ^b	Cycle 1, Day 1 Nivolumab + Ipilimumab		Cycle 1, Day 15 Nivolumab		Cycle 1 Day 29 Nivolumab	
Arm B: ^a EXTREME Regimen Cetuximab 400 mg/m ² initial dose then 250 mg/m ² weekly + Cis or Carbo + 5-FU Every 3 weeks for up to 6 Cycles followed by 250 mg/m ² Cetuximab weekly ^c 1 hour infusions	Cycle 1, Day 1 Cetuximab 2 hr infusion + Cis or Carbo 1 hr infusion + 5-FU (for 4 days, Day 1, 2, 3, 4)	Cycle 1, Day 8 Cetuximab 1 hr infusion	Cycle 1, Day 15 Cetuximab 1 hr infusion	Cycle 2, Day 1 Cetuximab 1 hr infusion + Cis or Carbo 1 hr infusion + 5-FU (for 4 days, Day 1, 2, 3, 4)	Cycle 2, Day 8 Cetuximab 1 hr infusion	Cycle 2, Day 15 Cetuximab 1 hr infusion

^a Arm A: Both nivolumab and ipilimumab should be administered as 30 minute infusions. Nivolumab is to be administered first. The second infusion will be ipilimumab and will start at least 30 minutes after completion of the nivolumab infusion

Arm B: Cetuximab is administered first followed by Cisplatin 100 mg/m² or Carboplatin (AUC 5) starting at least 1 hour after the completion of the Cetuximab infusion. 5-FU dose is 1000 mg/m² day 1 to day 4 (rounding of dosing for 5-FU is permitted per institutional standards).

^b Continues until disease progression, discontinuation due to unacceptable toxicity, withdrawal of consent, 24 months maximum from the first study treatment, or study closure

^c Cetuximab maintenance may be administered every 2 weeks, per local prescribing information.

^d ± 3 Days window applies to Arm A only

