4.5.1 Dosing

4.5.1.1 Nivolumab plus Ipilimumab (Arm A)

Participants randomized to Arm A will receive treatment with nivolumab 3 mg/kg every 2 weeks as a 30-minute infusion and ipilimumab 1 mg/kg every 6 weeks as a 30-minute infusion, starting on Day 1, until progression, unacceptable toxicity, withdrawal of consent, the study ends, or a maximum of 24 months from the first study treatment, whichever occurs first.

When nivolumab and ipilimumab are to be administered on the same day, separate infusion bags and filters must be used for each infusion. Nivolumab is to be administered first. The second infusion will always be ipilimumab and will start no sooner than 30 minutes after completion of the nivolumab infusion. Participants who require small volumes may infuse over < 30 minutes but no less than 20 minutes. The second infusion will always be the ipilimumab study treatment and will start after the infusion line has been flushed, filters changed and participant has been observed to ensure no infusion reaction has occurred.

Nivolumab and ipilimumab may be diluted in 0.9% Sodium Chloride Solution or 5% Dextrose solution.

Dosing calculations should be based on the body weight. If the participant's weight on the day of dosing differs by > 10% from the weight used to calculate the prior dose, the dose must be recalculated. All doses should be rounded to the nearest milligram. There will be no dose modifications allowed for both nivolumab and ipilimumab.

Participants may be dosed with nivolumab no less than 12 days from the previous dose. There are no premedications recommended for the first dose of study drug.

Participants should be carefully monitored for infusion reactions during nivolumab administration. If an acute infusion reaction is noted, participants should be managed according to [Section 4.5.8](#)

Doses of nivolumab may be interrupted, delayed, or discontinued depending on how well the participant tolerates the treatment. Dosing visits are not skipped, only delayed.

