8.2 Populations for Analyses

- All Enrolled Participants: All participants who signed an informed consent form and were registered into the IVRS.

- All Randomized Participants: All enrolled participants who were randomized to either treatment arm.
- All Randomized PD-L1 CPS ≥ 20 Participants: All randomized participants with PD-L1 CPS ≥ 20
- All Randomized PD-L1 CPS ≥ 1 Participants: All randomized participants with PD-L1 CPS ≥ 1 .
- All Treated Participants: All participants who received at least one dose of nivolumab, ipilimumab, cetuximab, cisplatin, carboplatin or 5-FU.
- Treated Participants with PD-L1 CPS ≥ 20 : All participants who received at least one dose of nivolumab, ipilimumab, cetuximab, cisplatin, carboplatin or 5-FU and have PD-L1 CPS ≥ 20 at baseline.
- All PK Participants: All participants with available serum time-concentration data
- Immunogenicity Evaluable Participants:
 - Nivolumab ADA Evaluable Participants: all treated participants with baseline and at least 1 post-baseline pre-infusion nivolumab immunogenicity assessment.
 - Ipilimumab ADA Evaluable Participants: all treated participants with baseline and at least 1 post-baseline pre-infusion ipilimumab immunogenicity assessment.
- All PD-L1 Tested participants: All participants, randomized or not, who had a tumor biopsy specimen available for tumor cell expression testing. This includes both randomized and screen failure participants.

Key analyses of study conduct, demographics, and efficacy will be done on the all randomized population and repeated on the randomized PD-L1 CPS ≥ 20 population. Participants in these analyses will be grouped as assigned at randomization.

Key analyses of exposure and safety will be done on the all treated population and repeated on the treated PD-L1 CPS ≥ 20 population. Participants in these analyses will be grouped by treatment received rather than treatment assigned at randomization. (Treatment arm received will be equal to treatment arm as randomized, unless the participant received the non-assigned regimen for all doses.)

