ADA should be tested using sensitive and valid methods and employing an appropriate strategy for elucidating immunogenicity. Detection of ADA is typically performed in three tiers (screening, confirmatory, and titer) using statistically determined cutpoints and samples testing positive in the ADA assay are analyzed for neutralizing activity, especially in late-stage clinical studies. "Detection" of ADA implies that drug-specific ADA was confirmed. The 'drug tolerance' of an assay (highest drug concentration that does not interfere in the ADA detection method) is not an absolute value and differs between individuals due to the varying avidities of ADA immune responses. An ADA sampling strategy of collecting samples at times when the least drug concentration is anticipated (trough concentrations) can increase the likelihood of accurate ADA detection.

It is useful to present ADA results from clinical studies as (a) characteristics of the ADA immune response, (b) relationship of ADA with pharmacokinetics (PK) and, when relevant, pharmacodynamics (PD) biomarkers, and (c) relationship of ADA with clinical safety and efficacy.

Clinical consequences of ADA can range from no apparent clinical effect to lack of efficacy (primary treatment failure), loss of efficacy (secondary treatment failure) or heightened effect due to

altered exposure to the biologic drug, adverse drug reactions (administration-related systemic or site reactions), and severe adverse drug reactions (anaphylaxis and unique clinical problems associated with cross-reactivity and neutralization of endogenous molecules). Thus it becomes important to examine any associations between ADA or any of its attributes with the various clinical sequelae. The presence of ADA may or may not preclude the administration of drug to ADA-positive subjects because the outcome is dependent upon the magnitude of the impact of ADA on PK and PD. Hence, the relationship of ADA with PK/PD is an important additional consideration, but does not necessarily result in a clinically impactful consequence per se.

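### With dosing on schedule, every post-baseline ipilimumab ADA sample, and every ipilimumab PK sample after C1D1, is drawn mid-interval on Day 15; none is at ipilimumab trough

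*Protocol*

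**What the plan says.** **Dosing.** Protocol 4.5.1.1 gives "ipilimumab 1 mg/kg every 6 weeks as a 30-minute infusion, starting on Day 1", and an Arm A cycle is 6 weeks. The dosing table in Protocol 4.5 shows the mid-cycle visit as "Cycle 1, Day 15 Nivolumab", with no ipilimumab.

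**Sampling.** Table 5.5-1 (Protocol 5.5) takes a predose sample for both drugs at C1D1, which is the baseline. Post-baseline PK and ADA samples for both drugs follow at C1D15, C2D15 and C4D15, and then on "D15 of every 4th cycle after C4D15 until end of study treatment or maximum up to two years of treatment". Footnote b defines predose as before the first drug given that day. There is one further ipilimumab PK sample, without ADA, on C1D1. Footnote c says of it: "This sample should be collected at the end of infusion of the second drug administered". The second drug is always ipilimumab. Under footnote a, if ipilimumab is stopped and nivolumab continues, ipilimumab samples are taken at the next two time points only.

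**Guidance on timing.** SAP Appendix 3 says that "collecting samples at times when the least drug concentration is anticipated (trough concentrations) can increase the likelihood of accurate ADA detection".

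**Evaluable population.** Protocol 8.2 defines the ipilimumab ADA-evaluable set as "all treated participants with baseline and at least 1 post-baseline pre-infusion ipilimumab immunogenicity assessment", and SAP 6.3 does the same. SAP Appendix 3 asks only for a baseline and one post-baseline assessment. It derives subject-level status from adequate samples, with 1-hour post-infusion samples given as an example of what to exclude.

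**The concern.** The sampling days are at trough for nivolumab, which is given every 2 weeks, and are applied unchanged to ipilimumab, which is given every 6. For ipilimumab they fall mid-interval. Circulating drug can interfere with ADA detection, which is why SAP Appendix 3 discusses drug tolerance and trough sampling.

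The comparison is also uneven. The baseline sample is drawn before any ipilimumab. Post-baseline positivity (seroconversion, or a titer at least 4-fold above a positive baseline) must then be found in serum that still contains drug above trough. If antibodies are masked, ipilimumab ADA incidence (SAP 7.6.14) would be too low, and some subjects would be misclassified in the displays of ADA status against safety and efficacy.

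For PK, on-schedule ipilimumab samples after C1D1 all sit at one point of the dosing interval. Days 15 to 42 after a dose are not observed in this trial, although SAP 7.7 plans ipilimumab population PK.

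**Working it through.** **Inputs.** Cycle length 42 days; ipilimumab on Day 1; nivolumab on Days 1, 15 and 29 (Protocol 4.5). Sampling cycles 1, 2, 4, then every 4th (Table 5.5-1). Maximum treatment 24 months, about 730 days.

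**1. Reproduce the table's own labels.** The nivolumab dose number at Day 15 of cycle c is 3(c − 1) + 2. For c = 1, 2 and 4 this gives 2, 5 and 11, matching the dose numbers in Table 5.5-1.

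**2. Place each sample.** Study day = 42(c − 1) + 15. Time since the ipilimumab dose = 15 − 1 = 14 days. Time to the next = 42 − 14 = 28 days.

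| Cycle | Study day | Days since ipilimumab | Days to next ipilimumab |
|---|---|---|---|
| 1 | 15 | 14 | 28 |
| 2 | 57 | 14 | 28 |
| 4 | 141 | 14 | 28 |
| 8 | 309 | 14 | 28 |
| 12 | 477 | 14 | 28 |
| 16 | 645 | 14 | 28 |

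C20D15 would be day 813, past 24 months. All six samples lie one third of the way through the interval (14/42), and none of the six is at ipilimumab trough. Ipilimumab PK has these six plus the C1D1 end-of-infusion sample.

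**3. Size of the difference.** No ipilimumab half-life is given; Protocol 3.3.1 gives one for nivolumab only (up to 25 days). Assuming single-exponential decline with half-life h, the day-14 level divided by the day-42 level is 2^(28/h).

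| Assumed h (days) | Ratio |
|---|---|
| 10 | 7.0 |
| 15 | 3.6 |
| 20 | 2.6 |
| 25 | 2.2 |

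**4. Samples off this pattern.** Dose delays shift the gap. After ipilimumab is stopped, the footnote a samples can be much later. If ipilimumab is withheld from C2D1, the next two points are days 57 and 141, which are 56 and 140 days after the day-1 dose. If it is withheld from C5D1, the last dose was on day 127 and the next two points are days 309 and 477, which are 182 and 350 days later.

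**5. The alternative day.** Day 1 of a later cycle is 42 days after the previous ipilimumab dose and 43 − 29 = 14 days after the previous nivolumab dose. Both drugs are at trough. The same cycles give days 43, 127, 295, 463 and 631 (C2, C4, C8, C12, C16). With C1D15 retained, that is again six sampling occasions.

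**The case against.** Day 15 has a practical logic: one draw serves both drugs and is at nivolumab trough. Immunogenicity and PK are exploratory, the ADA outputs are descriptive, and mid-interval samples are useful to a population PK model. The SAP sentence on trough sampling is background, introduced as a summary of regulatory guidance and a white paper. It says trough sampling can help and sets no rule for this trial, so the table breaches no stated requirement. All of that stands.

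There is also a partial fallback. Serum for soluble biomarkers is drawn at week 7, which is C2D1 in Arm A, and Protocol 5.5 allows biomarker serum to be used for ADA if required. That use is contingent, and Table 5.6-1 does not mark this serum as predose, so it reduces the gap without closing it.

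Four stronger readings are tempting, and the documents do not support them:

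- *Every post-baseline ipilimumab PK sample is on Day 15.* The C1D1 end-of-infusion sample is not.
- *The ipilimumab ADA-evaluable population is empty, because no scheduled post-baseline sample precedes an ipilimumab infusion.* SAP Appendix 3 defines the population without the pre-infusion condition, and footnote b makes predose relative to the first drug that day. What remains is inconsistent wording.
- *The plan needs an observed ipilimumab trough for its exposure analyses.* Protocol 8.4.4 mentions trough among model-derived exposure measures, in a sentence about nivolumab PK, and SAP 7.7 names no ipilimumab trough.
- *Drug levels are high and ADA incidence is biased low.* No ipilimumab concentration, half-life or assay tolerance is given. A ratio of levels cannot show masking, which depends on the absolute concentration against the assay's tolerance.

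**Conclusion.** The scheduling point holds. With ipilimumab ongoing and no delays, none of the six post-baseline ipilimumab ADA samples, and no ipilimumab PK sample after C1D1, is at ipilimumab trough. This departs from the sampling strategy that the SAP itself describes. The level at sampling is above trough by a factor of about 2.2 to 7.0, on the assumption of a 10 to 25 day half-life and single-exponential decline. Underestimation of ipilimumab ADA incidence is a possibility, not an established result. The later samples after ipilimumab is stopped come only from participants who discontinued it, so they do not stand in for those continuing both drugs. The primary and secondary efficacy analyses are untouched. This is an inexpensive improvement to exploratory results.

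**What to change.** In Table 5.5-1, move the predose PK and ADA samples after cycle 1 from Day 15 to Day 1 of the same cycles: C2D1, C4D1, then Day 1 of every 4th cycle. Keep C1D15 for PK. Leaving its ADA draw in place as well would avoid losing participants who stop before C2D1 from the evaluable set.

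In Protocol 8.2 and SAP 6.3, align the pre-infusion condition with SAP Appendix 3, and state which drug's infusion is meant if the condition is kept.

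The cost is a change to the table and the laboratory manual. No visit or blood draw is added, because Day 1 is already a dosing visit for both drugs. What is lost is the mid-interval ipilimumab PK points after cycle 1. For samples already taken on Day 15, each ADA result has an ipilimumab concentration from the same time point. Reporting the two together against the assay's drug tolerance would show whether masking is plausible.

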5.6 Biomarker Assessments

A variety of factors that could potentially predict clinical response to nivolumab in combination with ipilimumab will be investigated in peripheral blood and in tumor specimens taken from all participants prior to- and on-treatment and as outlined in Table 5.6-1. Data from these investigations will be evaluated for associations with response, survival (OS, PFS) and/or safety (adverse event) data. In addition, analyses of markers between the treatment arms will provide the necessary data to identify and validate biomarkers with predictive vs. prognostic value. All samples collected may also be used for future exploratory analyses (unless restricted by local requirements) to assess biomarkers associated with SCCHN or immunotherapy treatment. Complete instructions on the collection, processing, handling and shipment of all samples described herein will be provided in a separate procedure manual.

Table 5.6-1: Biomarker Sample Collection Schedule (Arms A and B):						
Study Day	Serum ^a	Plasma ^a	Whole Blood		Tumor ^{b,c}	Saliva
	Soluble Biomarkers	ctDNA	Gene expression	SNP	Biopsy	Oral microbiome
Screening					X	
D1	X	X	X	X (pre-dose)		X (pre-dose)
W3,D1 ^d	X	X	X			
W7,D1 ^d	X	X	X		X ^e	X
W15,D1 ^d	X	X	X			
Progression ^e	X ^f	X ^f	X ^f		X ^f	

^a Plasma, serum and whole blood should be collected on all patients on study, including active and newly enrolled patients.

^b All tumor samples may be obtained \pm 7 days of the indicated time.

^c Tumor sample prior to therapy is mandatory. If a recent tumor sample (obtained within 6 months of enrollment) is not available at screening, a fresh biopsy will be taken at any point prior to randomization obtained from core biopsy, punch biopsy, excisional biopsy or surgical specimen

^d The Biomarker week collections correspond to the following Cycle visits: W3D1 corresponds to C1D15 for treatment Arms A and B (in cases of no dose delays) W7D1 corresponds to C2D1 for Arm A and C3D1 for Arm B (in cases of no dose delays). W15D1 corresponds to C3D15 for Arm A and C5D15 for Arm B (in cases of no dose delays). Blood samples can follow Cycle visits in cases of dose delays, however the Week 7 biopsy should be collected at week 7 irrespective of dosing delays.

^e Week 7 (\pm 7days) Biopsy is optional. If progression occurs within 6 months from first dose and a week 7 biopsy was done, then biopsy samples upon progression (\pm 7 days) are optional. If progression occurs at greater than 6 months from first dose then progression biopsy is required. On study biopsies should be done if deemed medically safe per investigators judgement.

^f For samples at progression, the timing of this collection should be after the participant has come off study medication and before they have started new therapy (subsequent anti-cancer therapy). For participants that have consented to be treated beyond progression, it is better to wait to perform the biopsy after further progression of the disease, after they have come off study therapy and before they have started new therapy (subsequent anti-cancer therapy).

